9.3. Evaluation of Adverse Events

The investigator must assign the following AE attributes:

- AE diagnosis or syndrome(s), if known (if not known, signs or symptoms)
- Dates of onset and resolution (if resolved)
- Severity [and/or toxicity per protocol]
- Assessment of relatedness to the IP
- Assessment of relatedness to protocol-required procedures
- Action taken

The AE toxicity grading scale used will be the NCI CTCAE Version 4.03.

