A phase 1/2 investigation of safety/efficacy of nivolumab (Opdivo®) and ABI-009 (*nab*-rapamycin) in patients with advanced Ewing's sarcoma, PEComa, epithelioid sarcoma, desmoid tumor, chordoma, non-small cell lung cancer, small cell lung cancer, urethelial carcinoma, melanoma, renal cell carcinoma, squamous cell carcinoma of head and neck, hepatocellular carcinoma, classical Hodgkin's lymphoma, MSI-H/dMMR metastatic colorectal cancer, and tumors with genetic mutations sensitive to mTOR inhibitors

Study Number: SOC-1701

Study Phase: 1/2

Name of Investigational Product (IP)

ABI-009, rapamycin protein-bound nanoparticles for injectable suspension (albumin bound), *nab*-rapamycin, nanoparticle albumin-bound rapamycin

Name of FDA Approved Study Agent

Nivolumab (Opdivo®), is a programmed death receptor-1 (PD-1) blocking monoclonal antibody indicated for the treatment of patients with (1) BRAF V600 wild-type unresectable or metastatic melanoma, as a single agent, (2) BRAF V600 mutation-positive unresectable or metastatic melanoma, as a single agent. This indication is approved under accelerated approval based on progression free survival. (3) Unresectable or metastatic melanoma, in combination with ipilimumab, (4) Metastatic non-small cell lung cancer and progression on or after platinum-based chemotherapy, (5) Advanced renal cell carcinoma who have received prior anti-angiogenic therapy, (6) Classical Hodgkin lymphoma that has relapsed or progressed after autologous hematopoietic stem cell transplantation (HSCT) and post-transplantation brentuximab vedotin, (7) Recurrent or metastatic squamous cell carcinoma of the head and neck with disease progression on or after a platinum-based therapy, and (8) advanced or metastatic urothelial carcinoma who have progressed on platinum-containing chemotherapy.

Indication

Previously treated patients with advanced (metastatic or locally advanced) sarcoma, including desmoid tumor and chordoma

Objectives

Primary Objective

The primary objective of this study is to investigate the maximum tolerated dose of ABI-009, an mTOR inhibitor, when given sequentially with nivolumab in advanced UPS, LPS, OS, CS, Ewing's sarcoma.

Secondary Objectives

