Follow-up period is the on-study time period after the EOT Visit. All patients that discontinue study drug and have not withdrawn full consent to participate in the study will continue in the follow-up phase for survival and initiation anticancer therapy. Follow up will continue approximately every 12 weeks (+/- 3 weeks), until death, withdrawal of consent, or the study closes, whichever is the earliest. This evaluation may be made by record review and/or telephone contact.

Study Treatment

Patients will receive nivolumab 3 mg/kg as IV infusion over 30 min every 3 weeks (Day 1 of every 21-day cycle), followed by escalating doses of ABI-009 30, 45, 75 mg/m² for 2 of every 3 weeks by IV infusion over 30 minutes. ABI-009 dosing will start after 2nd nivolumab dose and to be administered on Day 8 and Day 15 of every cycle beginning in Cycle 2. Patients will continue therapy until unequivocal clinical disease progression, unacceptable toxicity, or until in the opinion of the investigator the patient is no longer benefiting from therapy, or at the patient's discretion.

Overview of Key Safety Assessments

Safety and tolerability will be monitored through continuous reporting of treatment-emergent and treatment-related adverse events (AEs), AEs of special interest, laboratory abnormalities, and incidence of patients experiencing dose modifications, dose delay/dose not given, dose interruptions, and/or premature discontinuation of IP due to an AE. All AEs will be recorded by the investigator from the time the patient signs informed consent until 28 days after the last dose of IP. Adverse events will be graded by National Cancer Institute (NCI) Common Terminology Criteria for Adverse Events (CTCAE) v4.03.

Physical examination, vital signs, laboratory assessments (e.g., serum chemistry, hematology), and ECOG performance status will be monitored. All SAEs (regardless of relationship to IP) will be followed until resolution. Local laboratory analysis will be performed as per study schedule.

The MTD for ABI-009 will be determined, and will be used in the Phase 2 part of the study.

Overview of Key Efficacy Assessments

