6.3.2. Dosage Adjustments, Delays, Rules for Withholding or Restarting, Permanent Discontinuation

Resume nivolumab in patients whose adverse reactions recover to Grade 0-1.

Permanently discontinue nivolumab for any of the following:

- Any life-threatening or Grade 4 adverse reaction
- Grade 3 or 4 pneumonitis
- Grade 4 colitis
- AST or ALT greater than 5 times ULN or total bilirubin greater than 3 times ULN
- Creatinine greater than 6 times ULN
- Any severe or Grade 3 treatment-related adverse reaction that recurs
- Inability to reduce corticosteroid dose to 10 mg or less of prednisone or equivalent per day within 12 weeks
- Persistent Grade 2 or 3 treatment-related adverse reactions that do not recover to Grade 0-1 within 12 weeks after last dose of nivolumab

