8.2. Safety Analysis

Demographic and baseline information (e.g., extent of prior therapy) on study patients will be tabulated. The number of patients studied for the Phase 1 part of study could range from 12 to 18 evaluable patients, and 22-28 evaluable patients for the Phase 2 part of the study.

For the Phase 1 part of the study, the following information will be reported for adverse events observed in the study: dose level, type (organ affected or laboratory determination, such as absolute neutrophil count), severity (by NCI Common Terminology Criteria for Adverse Events (CTCAE) Version 4.03 and most extreme abnormal values for laboratory determinations) and relatedness to study treatment. For each dose the number and percentage of patients experiencing any grade 3, 4, or 5 adverse event will be reported, as well as the number and percentage of patients who experienced selected specific types of adverse events. In addition, the DLTs will be summarized by dose level and the MTD will be determined.

The following table gives the probability of dose escalation at a single dose level as a function of the true probability of DLT at that level using the cohorts of 3 design (Objective #1) (2).

Table 1. Probability of Dose Escalation

True Rate of DLT (%)	Probability of Dose Escalation
10	0.91
20	0.71
30	0.49
40	0.31
50	0.17

For the Phase 2 part of the study, the entire treated population (Full Analysis Set) will be the analysis population for all safety analyses. Adverse events will be coded using the NIH CTCAE v4.03. Summary tables will include the number and percentage of patients with AEs, serious AEs, fatal AEs and other AEs of interest. Safety will be analyzed in all patient groups together (metastatic and locally advanced). Although this study will not be large enough to allow firm conclusions about safety or efficacy, it will provide preliminary data on safety and efficacy that will be useful in planning future studies. Frequency tables, graphs, and summary statistics will be used for outcome data.

Patient incidence of all treatment-emergent AEs will be tabulated. Tables of fatal adverse events, serious adverse events, treatment-related AEs, and adverse events leading to withdrawal from investigation product will also be provided.

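### Drug causality is collected only against the IP, named as ABI-009, while the analysis plans treatment-related tables for a two-drug regimen, so nivolumab events may be omitted or misattributed

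*Combined protocol and SAP*

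**What the plan says.** The synopsis opens with "Name of Investigational Product (IP"), under which only ABI-009 appears. Nivolumab has its own label, "Name of FDA Approved Study Agent".

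Section 9.3 requires two causality judgements for each event: "Assessment of relatedness to the IP" and "Assessment of relatedness to protocol-required procedures". It also asks for the action taken, without naming a drug.

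Section 8.2 uses a different term. Phase 1 events are to be reported by relatedness to study treatment, and a table of treatment-related events is planned. On stopping for toxicity the wording returns to the investigational product: "and adverse events leading to withdrawal from investigation product will also be provided". The synopsis (Overview of Key Safety Assessments) likewise ends its list of monitored outcomes with "premature discontinuation of IP due to an AE".

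For late events, the text under Section 9.2 records all AEs until 28 days after the last ABI-009 dose. After that it takes only SAEs suspected to be related to the IP. Section 9.4.2 repeats this rule, with the 28 days counted from the last dose of IP.

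**The concern.** The causality item to be collected and the causality variable to be reported are not the same thing. In a trial whose Phase 2 part is meant to assess the safety of a combination, the reader of the report will want to know which events were attributed to either drug, and to which one. If an investigator applies the IP definition literally, an immune-mediated event judged to be due to nivolumab is recorded as unrelated to the IP, and nothing else on the Section 9.3 list marks it as drug-related. A treatment-related table built from that item would not show it.

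The same wording governs two further outputs: which late SAEs are collected at all, and which AE-driven discontinuations are tabulated. Attribution that is not recorded at the time of the event is hard to reconstruct later.

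**Working it through.** The documents give no figure to reproduce on this point. The check sets passages side by side and adds one piece of schedule arithmetic.

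**1. What does IP mean?**

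- Narrow (ABI-009 only): the synopsis labels; Section 9.2, which ends the AE window at the last ABI-009 dose where the synopsis and Section 9.4.2 say IP; Section 9.2 again, which sends the reader to Section 6.2.3 for overdose of the IP, where only ABI-009 is covered; and Section 10.3, which distinguishes the IP from other protocol-required therapies.
- Wide (either drug): the definition of Study Day 1 as the first day of IP, although only nivolumab is given then; and the nivolumab accountability text in Section 7.2.

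The weight of the text favours the narrow meaning, but usage is not uniform.

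**2. Does either meaning give what Section 8.2 needs?**

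| Reading of IP | What the Section 9.3 item records | Consequence |
|---|---|---|
| ABI-009 only | Relatedness to ABI-009 | Events due to nivolumab alone are unrelated, so the treatment-related table may omit them |
| Either drug | Relatedness to the pair | Events are counted but cannot be attributed to one drug |

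The protocol itself needs attribution at both levels. Table 5 applies to events possibly related to ABI-009. Section 6.3.2 stops nivolumab for "Any severe or Grade 3 treatment-related adverse reaction that recurs".

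**3. The nivolumab-only period.** Cycles last 21 days, nivolumab is given on Day 1, and ABI-009 starts on Day 8 of Cycle 2 (Section 6.1).

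- Cycle 2 Day 1 = 21 + 1 = study day 22.
- Cycle 2 Day 8 = 21 + 8 = study day 29.
- Days on which only nivolumab of the two drugs has been given: 29 − 1 = 28 (days 1 to 28, doses on days 1 and 22), if there is no delay.

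On the narrow reading, no event with onset in those 28 days can be caused by the IP, however clearly nivolumab caused it.

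**4. Late SAEs.** After the 28-day window, collection depends on suspected relatedness to the IP. On the narrow reading, a late SAE suspected to be due to nivolumab alone does not qualify. Section 1.3.3 says immune-mediated reactions may occur after nivolumab is stopped. It cites 2 of 6 immune-mediated pneumonitis cases and 3 of 6 immune-mediated colitis cases diagnosed after discontinuation. It does not say how long after, so the share beyond 28 days is unknown.

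**5. Discontinuation.** The one AE-withdrawal table in Section 8.2 is for the investigational product, and Section 10.1 lists reasons for stopping the IP only. Exposure summaries cover both drugs (doses, average dose, duration) but not why a drug was stopped. No table of AEs leading to nivolumab discontinuation is specified.

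**The case against.** The strongest reply is that the defect is one of vocabulary. The planned table is headed treatment-related, not IP-related. No text equates the two or says that a nivolumab reaction is coded as unrelated. The case report form is not in the documents and may already have two fields. The term IP is used loosely enough that site staff could read it as covering both drugs. This stands in part: omission is a risk created by the wording, not a stated rule. It does not remove the point, because Section 9.3 is the only list of causality data in the protocol, and neither reading of IP supports attribution by drug.

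The reply is also right on several stronger inferences that a reader might draw:

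- **That DLT counts, and so the MTD, are biased.** The DLT note in Section 2.3 lists toxicities by type and grade and sets no relatedness condition. The Section 9.3 item does not decide what counts as a DLT.
- **That nivolumab events vanish from the report.** Section 8.2 plans tables of all treatment-emergent, serious and fatal events without a causality filter, and of Grade 3 to 5 events by dose. What is at risk in those is attribution. The exception is the late SAEs, which may not be collected.
- **That nivolumab delays go unreported.** In the synopsis the reference to the IP can be read as attached only to the last item, discontinuation, so delays and interruptions are not clearly limited to ABI-009. The action-taken item is not tied to one drug either.
- **That the number of missed patients can be computed.** Section 1.3.3 cites Grade 3-4 reactions in 42% and discontinuation for adverse reactions in 9% on nivolumab. With 12 + 22 = 34 to 18 + 28 = 46 patients, that gives 0.42 × 34 = 14.3 to 0.42 × 46 = 19.3, and 0.09 × 34 = 3.1 to 0.09 × 46 = 4.1. These are at most ceilings on the patients exposed to the problem. They come from melanoma patients dosed every 2 weeks, not every 3, and some events would be attributed to both drugs. Grade 3-4 events would still be in the all-causality reporting.

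**Conclusion.** The point holds as a mismatch between the causality item collected (IP) and the variable to be reported (study treatment), with three consequences: possible omission or misattribution of nivolumab events in treatment-related tables, non-collection of late SAEs suspected to be due to nivolumab alone, and no specified table of AEs leading to nivolumab discontinuation. The first two depend on the narrow reading of IP, which most of the text supports. On the wide reading the loss is attribution by drug.

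Its size in patients or events cannot be derived from the documents. What can be stated is the structure: 28 days of nivolumab alone for each patient on schedule, and every SAE after the 28-day window that is suspected to be due to nivolumab only.

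The view that on-treatment events survive in the all-causality tables assumes that treatment-emergent counts from the first dose of either drug, which the documents do not define. It also applies to patients in the Full Analysis Set, who have had at least one ABI-009 dose. The analyses are descriptive, so no error rate or power is at stake. The change should be made because it is cheap and bears on the main safety output of a combination study.

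**What to change.** - Define IP and study treatment once, and use each term consistently.
- In Section 9.3 and on the SAE form, record relatedness and action taken separately for ABI-009 and for nivolumab.
- Define treatment-related as related to either drug.
- In Sections 9.2 and 9.4.2, apply the late-SAE criterion to suspected relatedness to either drug.
- In Section 8.2 and the synopsis, tabulate related AEs and AE-driven discontinuation for each drug and for either.

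The cost is a few more form fields and table rows, plus an edit of the terms throughout the protocol. The reported treatment-related rate will be higher, because events attributed only to nivolumab will now count.

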9.4. Serious Adverse Events

9.4.1. Definition of Serious Adverse Events

An SAE is defined as an AE that meets at least 1 of the following serious criteria:

- fatal
- life-threatening (places the patient at immediate risk of death)
- requires in-patient hospitalization or prolongation of existing hospitalization
- results in persistent or significant disability/incapacity
- congenital anomaly/birth defect
- other medically important serious event

An AE would meet the criterion of "requires hospitalization", if the event necessitated an in-patient admission to a health care facility (eg, overnight stay).

If an investigator considers an event to be clinically important, but it does not meet any of the serious criteria, the event could be classified as an SAE under the criterion of "other medically important serious event". Examples of such events could include allergic bronchospasm, convulsions, blood dyscrasias, drug-induced liver injury, or events that necessitate an emergency room visit, outpatient surgery, or urgent intervention.

Since the criteria for the CTCAE grading scale differs from the regulatory criteria for SAEs, if AEs correspond to grade 4 "life threatening" CTCAE grading scale criteria

(eg, laboratory abnormality reported as grade 4 without manifestation of life threatening status), it will be left to the investigator's judgment to also report these abnormalities as SAEs. For any AE that applies to this situation, comprehensive documentation of the event's severity status must be recorded in the patient's medical record.

9.4.2. Reporting Procedures for Serious Adverse Events

All suspected unexpected serious adverse reactions (SUSARs) must be reported by the Investigator to their IRB in writing, and to the FDA within 7 days as required by law.

Any AE that meets any criterion for an SAE requires the completion of an SAE Report Form in addition to being recorded on the AE page/screen of the CRF. All SAEs must be reported to AADI Drug Safety within 24 hours of the investigator's knowledge of the event by facsimile, or other appropriate method, using the SAE Report Form, or approved equivalent form. This instruction pertains to initial SAE reports as well as any follow-up reports.

The investigator is required to ensure that the data on these forms is accurate and consistent. This requirement applies to all SAEs (regardless of relationship to IP) that occur during the study (from the time of signing of the informed consent form to 28 days after the last dose of IP), and those made known to the investigator at any time thereafter that are suspected of being related to IP.

The SAE report should provide a detailed description of the SAE and include a concise summary of hospital records and other relevant documents. If a patient died and an autopsy has been performed, copies of the autopsy report and death certificate are to be sent to AADI Drug Safety as soon as these become available. Any follow-up data will be detailed in a subsequent SAE Report Form, or approved equivalent form, and sent to AADI Drug Safety.

Where required by local legislation, the investigator is responsible for informing the IRB/EC of the SAE and providing them with all relevant initial and follow-up information about the event. The investigator must keep copies of all SAE information on file including correspondence with AADI and the IRB/EC.

9.5. Pregnancy and Breast Feeding Reporting

If a pregnancy occurs in a female patient, or female partner of a male patient, while the patient is taking protocol-required therapies, report the pregnancy to AADI as specified below. In addition to reporting any pregnancies occurring during the study, investigators should monitor for pregnancies that occur up to 3 months after the last dose of protocol-required therapies.

The investigator will follow the female patient until completion of the pregnancy, and must notify AADI Drug Safety immediately about the outcome of the pregnancy (either normal or abnormal outcome) using the Pregnancy Follow-up Report Form, or approved equivalent form. If a lactation case occurs while the female patient is taking protocol-required therapies, report the lactation case to AADI as specified below. In addition to reporting a lactation case during the study, investigators should monitor for lactation cases that occur up to 1 week after the last dose of protocol-required therapies.

10. WITHDRAWAL FROM TREATMENT, PROCEDURES, AND STUDY

10.1. Discontinuation from Investigational Product

The following events are considered sufficient reasons for discontinuing a patient from the IP:

- AE(s) (that are intolerable)
- Disease progression
- Physician decision
- Withdrawal of consent (from treatment only)
- Death
- Lost to follow up
- Protocol violation
- Other (to be specified on the CRF)

The reason for treatment discontinuation should be recorded in the CRF and in the source documents.

10.2. Discontinuation from the Study

The following events are considered sufficient reasons for discontinuing a patient from the study:

- Withdrawal of consent
- Death
- Lost to follow up
- Protocol violation
- Other (to be specified on the CRF)

The reason for study discontinuation should be recorded in the CRF and in the source documents.

At the time of withdrawal, it should be determined whether the patient is withdrawing from treatment alone, or from treatment and collection of further data (e.g., survival). Every effort should be made to collect survival data after patient withdraws from treatment.

Patients have the right to withdraw from the study at any time and for any reason without prejudice to his or her future medical care by the physician or at the institution.

10.3. Investigator or Sponsor Decision to Withdraw or Terminate Patient's Participation Prior to Study Completion

The investigator and/or sponsor can decide to withdraw a patient(s) from Investigational Product and/or other protocol-required therapies, protocol procedures, or the study as a whole at any time prior to study completion.

Patients may be eligible for continued treatment with AADI's Investigational Product and/or other protocol-required therapies by a separate protocol or as provided for by the local country's regulatory mechanism.

11. REGULATORY OBLIGATIONS

11.1. Informed Consent

An initial sample informed consent form is provided for the investigator to prepare the informed consent document to be used at his or her site. Updates to the template are to be communicated formally in writing from the investigator to AADI. The written informed consent document is to be prepared in the language(s) of the potential patient population.

Before a patient's participation in the clinical study, the investigator is responsible for obtaining written informed consent from the patient after adequate explanation of the aims, methods, anticipated benefits, and potential hazards of the study and before any protocol-specific screening procedures or the IP is administered.

The investigator is also responsible for asking the patient if the patient has a primary care physician and if the patient agrees to have his/her primary care physician informed of the patient's participation in the clinical study. If the patient agrees to such notification, the investigator is to inform the patient's primary care physician of the patient's participation in the clinical study. If the patient does not have a primary care physician and the investigator will be acting in that capacity, the investigator is to document such in the patient's medical record.

The acquisition of informed consent and the patient's agreement or refusal of his/her notification of the primary care physician is to be documented in the patient's medical records, and the informed consent form to be signed and personally dated by the patient or a legally acceptable representative and by the person who conducted the informed consent discussion. The original signed informed consent form is to be retained in accordance with institutional policy, and a copy of the signed consent form is to be provided to the patient or legally acceptable representative.

If a potential patient is illiterate or visually impaired and does not have a legally acceptable representative, the investigator must provide an impartial witness to read the informed consent form to the patient and must allow for questions. Thereafter, both the patient and the witness must sign the informed consent form to attest that informed consent was freely given and understood.

